# 2 Introduction

# 2.1 Background

Gastrin-releasing peptide (GRP), a bombesin-like peptide growth factor, regulates numerous functions of the gastrointestinal and central nervous systems, including release of gastrointestinal hormones, smooth muscle cell contraction, and epithelial cell proliferation. It is a potent mitogen for physiologic and neoplastic tissues, and it may be involved in growth dysregulation and carcinogenesis.

The effects of GRP are primarily mediated through binding to its receptor, the GRP receptor (GRPR), a G protein–coupled receptor originally isolated from a small cell lung cancer cell line. Upregulation of the pathway of GRP/GRPR has been reported in several cancers, including breast, prostate, uterus, ovaries, colon, pancreas, stomach, lung (small and non-small cell), head and neck squamous cell cancer and in various cerebral and neural tumours.

In breast cancer, GRPR overexpression can reach very high density according to tumour type (e.g. 70-90 % expression in ductal breast cancer specimens) [1]. GRPR are highly overexpressed in prostate cancer where studies in human prostate cancer cell-lines and xenograft models showed both high affinity (nM level) and high tumour uptake (%ID/g) but the relative expression of GRPR across evolving disease setting from early to late stage has not been fully elucidated yet [2]. In colorectal patients, presence of GRP and expression of GRPR have been determined by immunohistochemistry in randomly selected colon cancers samples, including LN and metastatic lesions. Over 80% of samples aberrantly expressed either GRP or GRPR, and over 60% expressing both GRP and GRPR, whereas expression was not observed in adjacent normal healthy epithelium [3].

GRP is physiologically present in pulmonary neuroendocrine cells and plays a role in stimulating lung development and maturation. However, it seems to also be involved in growth dysregulation and carcinogenesis. Stimulation of GRP leads to increasing the release of epidermal growth factor receptor (EGFR) ligands with subsequent activation of EGFR and mitogen-activated protein kinase downstream pathways. Using non–small cell lung cancer (NSCLC) cell lines it has been confirmed that EGF and GRP both stimulate NSCLC proliferation, and inhibition of either EGFR or GRPR resulted in cell death [4].

In nuclear medicine, peptide receptor agonists have long been the ligands of choice for tracer development and utilization. The rationale behind the use of agonist-based constructs laid on to receptor-radioligand complex internalization enabling the high accumulation of radioactivity inside the target cells. In case of radiometal-labelled peptides, the efficient receptor-mediated endocytosis in response to agonist stimulation provides high *in vivo* radioactivity uptake in targeted tissues, a crucial prerequisite for optimal imaging of malignancies. However, a paradigm shift occurred when receptor-selective peptide antagonists showed preferable biodistribution, including considerably greater *in vivo* tumour uptake, compared with highly potent agonists. A further advantage displayed by GRPR antagonists is a safer clinical use, not so much at tracer doses for the current diagnostic point of view, but in view of greater doses for potential therapeutic purposes, as the use of antagonists does not foresee acute biological adverse effects [5].

The Sponsor has therefore designed the current protocol to establish whether the ligand NeoBOMB1, a high affinity antagonist for GRPR, radiolabelled with a well-established PET isotope, Gallium-68 (Ga) is a suitable radiotracer for *in vivo* detection of GRPR-expressing malignancies, currently focusing on breast, prostate, lung (small cell and non-small cell) and colon-rectum.

# 2.2 Preclinical data

Bombesin was first isolated from the European frog Bombina bombina and was demonstrated to mimic the mammalian gastrin-releasing peptide (GRP) and neuromedin B (NMB)[6]. In non-clinical models, [Ga]-NeoBOMB1 have shown high affinity to the GRPR expressed in breast, prostate, and Gastro Intestinal Stromal Tumour (GIST), as well as a low degree of internalization upon binding to the specific receptor. The ability of the radiolabelled peptide to target the GRPR expressing tumour has been confirmed in *in vivo* imaging studies in both prostate cancer and GIST models.

# 2.3 Clinical data

# 2.3.1 Clinical studies performed with Bombesin analogues

Various bombesin-analogs have been studied in several entities, including both agonists and antagonists. The following summary tables (Table 1, 2, 3) provide the reference to each study.

Bombesin analogue	Indication	Dose	Summary of Results
[  Ga]-NeoBOMB1 (antagonist)	Prostate adenocarcinoma	60-339 MBq	First in man study – compassionate use program. Good tolerability, good sensitivity: visualization of liver micrometastatis and lymph- node metastases down to 5 mm in size (n=4). [7] See protocol section 2.3.2
[  Ga]-SB3* (antagonist)	Advanced prostate cancer (breast cancer also included) with progressing disease and history of previous therapy, including hormonal.	283.91±91 MBq 23±0.7 nmol (~35 μg)	17 pts (9 PC + 8 BC): 5 out of 9 (~55%) prostate cancer patients showed specific uptake. [8]

#### Table 1: Studies with in-human application of bombesin and its analogs in prostate cancer.

 F-BAY-86-4367	Drimony and	200±11 MP~	Eirot in man study DK/desimetry in
(antagonist)	Primary and recurrent prostate cancer	302±11 MBq	First in man study. PK/dosimetry in patients was good. Positive PET images in 3/5 with primary disease and 2/5 with biochemical relapse (n=10). [9]
 Cu-CB-TE2A- AR06 (antagonist)	newly diagnosed prostate cancer (T1c-T2b, GS 6-7) without prior therapy	184±51 MBq 14±4 μg	Phase I study. PK/dosimetry was ok. Three out of 4 tumours were visualized with high contrast. [10]
[  Ga]-BAY-86- 7548 (also called RM2) (antagonist)	histologically confirmed prostate adenocarcinoma or recurrent prostate cancer biochemically recurrent prostate cancer	147 MBq (median dose) ~20 μg	First in man study (n=14): sensitivity, specificity, and accuracy of 88%, 81% and 83%, respectively, for detection of primary PCa and sensitivity of 70% for metastatic LNs (histology as gold standard). [11] Pilot comparison of  Ga-RM2 and  Ga-PSMA-11 PET (n=7).  Ga- PSMA-11 had the highest physiologic uptake in the salivary glands and small bowel, with hepatobiliary and renal clearance, whereas  Ga-RM2 had the highest physiologic uptake in the pancreas, with renal clearance.  Ga-PSMA- 11 localized in a lymph node and seminal vesicle in a patient with no abnormal  Ga-RM2 uptake. Abdominal periaortic lymph nodes were more easily visualized by  Ga-RM2 in two patients because of lack of interference by radioactivity in the small intestine. [12]
99m Tc-HABBN (agonist)	biopsy-proven prostate cancer	549–688 MBq	SPECT/CT results were negative (most likely due to metabolic instability of the compound). GRPR expression confirmed by IHC. (n=8) [13]
99m Tc-[Leu13] BN (agonist)	Suspected or proven prostate cancer	185 MBq	Positive SPECT scans obtained in all 8 patients with cancer (total of 10 examined, 2 with benign adenoma). Invasion of pelvic LNs shown in 3 cases (confirmed at surgery). [14]
99m Tc-RP527 (agonist)	Metastasized prostate cancer	555 MBq	First in man study with bombesin analogue including 4 patients with metastasized PC. Specific uptake observed in 1 out of 4. [15]

	sy-proven tate cancer	111-142 MBq	Pre-surgical newly diagnosed prostate cancer patients (n=7). High physiologic uptake in the pancreas and quick renal clearance. High and specific uptake in primary cancer lesions was found. The SUVmean and SUVmax of tumour region is 4.22±1.33 and 4.64±2.53. Median tumour to background ratios was 15.29 (9.27-26.42). [16]
--	--------------------------	-------------	--

Bombesin	Indication	Dose	Summary of Results
analogue [  Ga]-BAY-86- 7548 (also called RM2) (antagonist)	biopsy-proven primary breast carcinoma	118 – 213 MBq (26 – 56 µg of peptide)	High contrast in 73% examined breast cancer patients (n=15). Sensitivity of 93% for ER-positive tumours, upstaging in 47% of patients. [17]
[  Ga]-SB3 (antagonist)	Advanced breast cancer (prostate cancer also included) with progressing disease and history of previous therapy	283.91±91 MBq 23±0.7 nmol (~35 μg)	Mixed patients with prostate (n=9) and breast (n=8) cancer: 4 out of 8 breast cancer patients showed specific uptake. [8]
99m Tc-Bombesin analogue (not specified)	Suspicious palpable breast lesions (with no definitive diagnosis in other imaging procedures)	370–444 MBq	SPECT/CT scan findings were positive in 19/33 patients. Pathologic examination confirmed breast carcinoma in 12 patients with positive scan. Sensitivity (100%); specificity (66.1%); negative (100%) and positive (63%) predictive values; accuracy (76%). [18]
99m Tc- EDDA/HYNIC- [Lys3]-BBN (agonist)	Early stage breast cancer and healthy volunteers.	na	Rapid blood clearance with mainly renal excretion. Good dosimetry. Well-differentiated concentration of tracer in cancer mammary tissue. [19]
99m Tc-RP527 (agonist)	Clinical diagnosis suggestive of breast carcinoma (n=9) and tamoxifen- resistant bone- metastasized	~555 MBq (max 3ng/kg)	Tracer uptake evident in the primary tumour in 8 out of 9 pts (88%) and in involved lymph nodes (confirmed by IHC). In the 5 patients with tamoxifen-resistant osseous disease, none (0/5) of the known

	breast carcinoma (n=5)		sites of osseous involvement were positive. [20]
99m Tc-[Leu13] BN (agonist)	breast cancers (T1b and T1c)	185-296 MBq (~0.7 mg)	The tracer detected all 5 breast cancers, with visualization of axillary nodes where present. When comparison with Sestamibi, BN analogue showed higher T/B. [21]

**Table 3**: Studies with in-human application of bombesin and its analogs in GIST and other types of cancer.

Bombesin	Indication	Dose	Summary of Results
analogue			
[  Ga]-NeoBOMB1 (antagonist) – AAA kit	GIST	150-250 MBq	See protocol section 2.3.2
[  Ga]-BZH3 (agonist)	Low Grade Gliomas	na	[  Ga]-bombesin and [  F]FDG- PET predicted correctly malignant transformation or recurrence of the initial tumour (n=9). [22]
[  Ga]-BZH3 (agonist)	GIST	150-210 MBq (~ 3 nmol)	Patients with GIST (n=17 scheduled for therapy with imatinib because of unresectable primary or recurrent GIST or because of metastatic disease). Dynamic PET scans comparison with [  F]FDG. FDG discovered 25/30 lesions, BZH3 8/30. Once, the lesion was seen with BZH3 and not with FDG. [23]
99m Tc-[Leu13] BN (agonist)	Colorectal cancer	na	13 (6 suspected colon cancer +7 known to have rectal cancer). Cancer detected in 11/13 and 2 false positives. 5/5 positive lymph nodes detected. Results confirmed by pathologic evaluation. [24]
[  Ga]-NOTA-Aca- BBN	Healthy volunteers Glioma diagnosed by MRI	111 ± 148 MBq	Healthy volunteers (n=4): no adverse symptoms being noticed or reported. Patients with glioma (n=12): all MRI-identified lesions showed high signal intensity on  Ga-

NOTA-Aca-BBN PET/CT; the
immunohistochemical staining
confirmed a positive correlation
between SUV and GRPR
expression level. [25]

## 2.3.2 [Ga]-NeoBOMB1 in GRPR-positive malignancies

The [Ga]-NeoBOMB1 formulation, is currently under clinical investigation at the Innsbruck University, Austria. This is a Phase I/IIa study to evaluate safety, biodistribution, dosimetry and preliminary diagnostic performance of [Ga]-NeoBOMB1 in patients with advanced TKI-treated GIST using positron-emission tomography/computer tomography (PET/CT).

An additional objective is to improve the diagnostic accuracy in GIST via PET/CT, including tumours with TKI-resistant subtypes. Better detection capability, classification and definition of lesion extent are expected from the use of [Ga]-NeoBOMB1.

Following completion of the phase-I part of the study (6 patients completed), the product was shown to present a favorable safety and tolerability profile, with no adverse events (AEs) related with the compound (interim report released in November 2017). Uptake in tumour was fast with good imaging performance already at 1h after administration (Figure 1), associated with rapid renal and blood clearance.

A005D-E01-201	

The locally c	ompounded	[68Ga]-NeoBOMB1	solution	has b	een tested	in the	frame	of a

The locally compounded [Ga]-NeoBOMB1 solution has been tested in the frame of a compassionate use program **and the second se** 

The formulation tested in **Exactly** is similar to the formulation developed by AAA: the drug substance is exactly the same, it's highly soluble and immediately bioavailable after CONFIDENTIAL v. 3.0 dated 05 July 2018 26/73

intravenous injection. It is also important to note that the final radiolabelled solution injected in patients is very similar for volume and pH in both cases, with the only exception of some excipients. The excipients used in the formulation developed by AAA (necessary to stabilize the product during lyophilisation, as well as to guarantee the long-term storage of the product) do not interact directly with the active substance and therefore do not have an impact on the disposition or clinical performance of the tracer.

# 2.4 Rationale and risks/benefits

The literature reports the GRPR overexpression in several malignant lesions but there is still a lack of precise data correlating GRPR overexpression to the molecular type of histological cancer as well as over the process of malignant transformation except for breast cancer [27]. In parallel, there are few studies focusing on GRPR imaging of primary tumours and metastatic lesions including lymph nodes. As there is a growing body of evidence suggesting that GRPR might be a valuable target for tumour identification and treatment, the Sponsor has conceived a study to investigate the diagnostic performance of NeoBOMB1, an antagonist with high affinity for GRPR, radioloabeled with a well-established PET isotope, Gallium-68 (Ga).

The Sponsor anticipates no biological effects of tracer dose (<50µg) of antagonist so no acute biological effects are expected. Regarding radioactivity, a dose of 3 MBg/kg ± 10% ranging within 150 to 250 MBq, is considered adequate to ensure appropriate imaging quality throughout the entire imaging protocol (latest time point at 4h p.i.) with Ga as radionuclide. This dose-range is in line with the recommended activity to obtain a good quality image for other DOTA-conjugated peptides)[26]. The phase I/IIa study currently ongoing at Innsbruck University is injecting patients using the dose described above. Data coming from Innsbruck (interim safety and imaging report) shows that the administration of 50µg [68Ga]-NeoBOMB1 in six patients diagnosed with GIST demonstrated good tolerability in all patients. No SAE was observed, and few minor side effects (fatigue, headache, lecocyturia, anemia) was observed in 2 patients with pre-existing conditions, with low probability to be causually related to the study drug administration. Pharmakokinetic analysis revealed a high in vivo stability and rapid renal excretion of [Ga]-NeoBOMB1 with highest accumulation in pancreas followed by kidney and liver. Overall these first clinical results shown both, a favourable safety profile and a preliminary good GRP-receptor targeting properties of [Ga]-NeoBOMB1, when administered at the standard gallium-68 low-radiation imaging dose. In terms of radioactive uptake kinetics, the interim report describes that following the administration of the compound there was a fast tumour-uptake, a rapid blood and renal clearance, which resulted in a good imaging performance as early as 60 minutes post-injection. In terms of dosimetry, the report describes a mean effective radiation dose of 0.026 mSv/MBg which is one-third lower than the calculated human-dose extrapolated from the animal model (0.039 mSv/MBq). With a maximum injected activity of 250 MBg the estimated effective dose would be 6.5 mSv per exam, which is lower that from the conventional [F]FDG-PET imaging.

The contribution of the low-dose CT is also to be contemplated. The amount of radiation dose from low-dose CT scan depends on different parameters, some related with the acquisition protocol (e.g. mA, mV), other intrinsic to the device used (e.g. single slice vs helical scanners). In the current protocol, to assess the pharmakcokinetic and the dosimetry of [Ga]-CONFIDENTIAL v. 3.0 dated 05 July 2018 27/73

NeoBOMB1, a maximum of 4 low-dose whole-body CT scans will be performed. An overall whole-body dose of maximum 7 mSv (from 4 to 7 mSv) per CT scan is expected.

For patients entering in the dosimetry group, a total theoretical radiation dose of 34,5 mSv is expected after administration of study drug plus the required four low-dose CT.. A total theoretical radiation dose of 20.5 mSv is expected for patients who will be included in the non-dosimetry group except for patients with PC who will receive an expected radiation dose of 27.5 mSv due to the additional CT scan required for them. In all the cases, the estimated effective dose will fall in the risk category level III as per the report 103 of the International Commission on Radiological Protection (ICRP) and are justified by a level of benefit as "Acquisition of knowledge, directly aimed at prevention or cure of serious disease". The standard radiation-exposure minimization measures including frequent bladder voiding is always a standard recommendation practice with radioligands presenting renal clearance, and is required in the current protocol. It is noteworthy reminding that this estimated total radiation dose is well aligned with the FDA recommendation of 30 mSv for adult research subjects receiving a single dose (Guidance for Industry and Researchers; "The Radioactive Drug Research Committee: Human Research without an Investigational New Drug Application", August 2010).

Another expected benefit of [Ga]-NeoBOMB1-PET relies on the potential early diagnostic detection of a recurrence, whether local relapse or distant metastasis, among those patients diagnosed with tumours expressing GRPR. Early and accurate detection translates in improved planning of treatment with classical therapeutic options, i.e. locoregional ablation techniques. Moreover, if [Ga]-NeoBOMB1 targets cancerous lesions with sufficient specificity and sensitivity, new treatment possibilities including peptide receptor radionuclide therapy may emerge.

In light of the disease status of the patients eligible for our study and the low risk of administration of [Ga]-NeoBOMB1, the benefit-risk balance is favourable and weights for patient's benefit.

# 3 Study design

# 3.1 Description of the study

## Rationale of the design:

This is a Phase II, multi-center, open label, single dose study in cancer patients with tumour types known to overexpress GRPR, including breast, prostate, colorectal, small-cell and non-small cell lung.

[figure not shown]
The main objective of the Phase II study is the characterization of the preliminary targeting properties of [Ga]-NeoBOMB1 in patients with malignancies known to overexpress GRPR to assess the tumour-background ratio. The secondary objectives of the clinical trial are safety and tolerability and dosimetry aspects. All the objectives, with the exception of the secondary one relative to biodistribution and dosimetry that will be assessed within the dosimetry group, will be assessed in the overall population (n=50). Analyses of the dosimetry group data will

lead to the optimal time window for PET/CT imaging for future clinical trials. However, in the case that the Sponsor obtains the results of the dosimetry and biodistribution assessments from at least 3 patients of the dosimetry group before the full completion of the study recruitment and the results show that the optimal time window is different from 1h30±30min or 2h30±30min as initially predicted by the Sponsor, the timepoints of the whole-body PET/CT scans for the remaining patients included in the non-dosimetry group will be adjusted.

#### Study conduct:

[figure not shown]
Population will be divided in two groups:

- Phase-II dosimetry group: 10 patients bearing breast and prostate cancer will undergo additional assessments to confirm previous data on tracer bio-distribution, radiation dosimetry, residence time for critical organs, and absorbed dose critical organs for [Ga]-NeoBOMB1. Serial venous whole blood and urine samples will be collected for pharmacokinetic characterization. Patients will undergo a 15-min-static whole-body PET images at 15 min p.i.at 1h±15 min, 2h±15 min and 4h±30 min to determine absorbed doses to normal organs and to target tumour lesions. Venous whole blood samples will be collected at pre-dose (0), 5, 10, 20, 30±5, 60±5 min, and at 2h±10 min and 3-4 h±10 min p.i. Urine samples from 0-2 h and from 2-4 h p.i. will also be collected.
- **Phase-II non-dosimetry group:** 40 patients will be enrolled in the second group. PETimaging will be reduced to 2 whole body scans at 1h30±30min and at 2h30±30min likely to be a 15-min static late PET for all tumour-types. Only prostate tumour patients will undergo an additional early 5-min static PET scan to better assess lymph node metastases (if applicable). Blood and urine sampling will be omitted.

A005D-E01-201		Page 30 of 73
---------------	--	---------------

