PET Imaging Data	
 
✓ SCLC: n=10
 
Patients included in the non-dosimetry group will undergo one early and one late whole-body PET-imaging acquisition, with no blood and urine sampling. Only prostate tumour patients will undergo an additional early 5-min static PET scan to better assess lymph node metastases (if applicable). GRPR expression must be assessed while the study is ongoing within 4 weeks after IMP injection by Immunohistochemistry staining from archival or recent biopsy specimens (not older than 6 months prior to IMP injection). The objectives of the study will be applicable for the whole study population with the exception of the secondary objective relative to the biodistribution and dosimetry that will be applicable only for the dosimetry group.
 

PET Imaging Data	The subjects enrolled in the dosimetry group will undergo 4 15-min static whole body PET scaps at 15 min, 1b+15 min, 2b+15 min, and at 4b+30 min
acquisition	
 
whole-body PET scans at 15 min, 1h±15 min, 2h±15 min and at 4h±30 min post injection (p.i.) to determine absorbed doses to normal organs and to target tumour lesions. Regions of Interest (ROIs) or Volumes of Interest (VOIs) will be drawn on the late whole-body PET images over the critical organs and tumour lesions to generate tissue time-activity curves (TACs), calculate the tumour-background ratio and assess the radioactivity residence times.
 
To determine blood activity curves, venous whole blood samples will be withdrawn (around 0, 5, 10, 20, 30, 60 min, 2 h and 3-4 h p.i.) and assessed
 

	via γ-counter for radioactivity measurements. Urine samples from 0-2 h and from 2-4 h p.i. will be collected and assessed via γ-counter for radioactivity measurements to complete dosimetry and biodistribution assessments. Urine samples will be saved, frozen for further metabolite assessments, at the Sponsor's decision. The subjects enrolled in the Phase II non-dosimetry group will undergo whole-body PET acquisitions at 1h30±30min and at 2h30±30min, likely to be a 15-min static PET for all tumour-types combined with a 5-min-static early-PET for prostate cancer.			
CT Imaging Data Acquisition	For all patients a low-dose CT will be combined to PET imaging.			
	Desimetry group:			
Data analysis,	Dosimetry group:			
biodistribution and	ROIs/VOIs for critical organs and tumour lesions will be drawn using the			

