### 4.1.6 Imaging

[Ga]-NeoBOMB1 imaging will be performed using a standard integrated PET/CT system. All imaging will be performed at the Department of Nuclear Medicine.

It is important to remember to record the patients' weight and height in the PET system software.

The patient must be hydrated per os with at least 750 mL of bottled drinking water 1 h before of image acquisition.

A standard PET/CT tomograph consists of a LSO PET system combined with a multi-row spiral CT system.

Immediately before the PET/CT examination, patients are requested to empty their bladder. Patients are positioned supine with raised arms and head-first on the common patient handling system in accordance with standard CT practice.

[figure not shown]
First, a topogram will be acquired over 1,024 mm axially. Coaxial whole-body imaging ranges will be defined on the topogram, covering an area from the skull to the mid-thighs (6-7 PET bed positions, or 90–110 cm, depending on the size of the patient). CT shall be performed for attenuation correction purposes and anatomical reference for subsequent PET acquisition. During the CT acquisition a limited breath hold protocol will be followed, which required the patients to hold their breath in normal expiration. After completion of the CT, patient's bed moves automatically to the PET gantry, where 3D PET emission scanning subsequently will starts in the caudocranial direction.

The administration of the radiotracer will be performed using a venous access, injection volume will be up to 5.5 ml with a slow bolus paradigm however conserving the same procedure time for all the patients. During this slow bolus, vital signs will be monitored. The radiolabeling protocol ensures that standard conditions are kept in terms of peptide mass.

In case of SAEs, the injection will be stopped immediately and reported based on the Toxicity Grading Scale in vaccine clinical trials.

Patients of the dosimetry group will undergo 4 sequential PET/CT scans. The IMP [Ga]-NeoBOMB1 injection should occur prior to the start of any imaging. Patients should be positioned and imaging should begin at 15min, 1h±15min, 2h±15min and 4h±30min post IMP injection with PET/CT scans consisting of low dose attenuation correction CT scans followed by PET images acquired from the head through the mid-thigh (approximately 6-7 beds

depending on patient height). PET data will be corrected for photon attenuation, dead-time, random events and scatter.

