### Figure 4: Dosimetry group PET imaging flow chart

WB PET/CT : low-dose for 4 WB PET/CT from the vertex to the upper thighs for attenuation correction followed by a total-body PET examination

Affinity parameters of the [Ga]-NeoBOMB1 (KD) will be used to create a model able to predict dose to tumour and relevant organs (pancreas, kidney, liver) expected to present the greatest relative tracer uptake when a bombesin antagonist (such as [Ga]-NeoBOMB1) is administered.

The images will be analysed with regards to the diagnostic suitability of [Ga]-NeoBOMB1 for tumour targeting as well as the safety of the procedure (whole body dosimetry of [Ga]-NeoBOMB1).

Patients of the **non-dosimetry group** will undergo 2 whole-body PET/CT scans at 90±30min and at 150±30 min. Patients with prostate cancer will also undergo a 5-min static PET/CT scan on relevant regions for lymph node imaging purpose (if applicable).

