#### 7.2 Evaluation of Targeting Properties by Standard Uptake Value (SUV)

Targeting properties of [Ga]-NeoBOMB1 will also be evaluated by PET imaging using tumor uptake. Tumor uptake will be evaluated by the Standard Uptake Value (SUV) at each lesion by PET Imaging. The maximum SUVmean and SUVmax (g/mL) of each lesion will be presented by the lesion location with summary statistics (n, mean  $\pm$  standard deviation, minimum, median, quartiles, and maximum) at scheduled time points overall and split by GRPR positive and negative patients, as well as by tumor type. Dosimetry and non-dosimetry group will be summarized separately due to different scheduled time points.

The 80% and 95% confidence intervals for difference in SUV (SUVmean and SUVmax) between GRPR positive and negative patients will be derived by Student's *t* distribution if normality assumption is adequate, or Wilcoxon Rank Sum method otherwise.

The Standard Uptake Value ratio (SUVr) at each time point will be calculated as the SUVmean of each lesion / the SUVmean of different regions as a reference and presented in a data listing.

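### The two non-dosimetry scan windows each span an hour and meet at 2 h, but SAP 7.2 analyses SUV by scheduled time point only, so scan timing is not separated from tumour-type or GRPR differences

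*Protocol*

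**What the plan says.** The Protocol synopsis gives the non-dosimetry group "one early and one late whole-body PET-imaging acquisition". Protocol 3.1 (Study conduct) sets these as "2 whole body scans at 1h30±30min and at 2h30±30min likely to be a 15-min static late PET", and Protocol 4.1.6 repeats that these patients "will undergo 2 whole-body PET/CT scans at 90±30min and at 150±30 min". The same times appear in Protocol 4.2.2 and 4.5. None of these places states a minimum interval between the two scans.

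SAP 7.2 presents lesion SUVmean and SUVmax with descriptive statistics ("quartiles, and maximum) at scheduled time points overall and split by GRPR positive and negative patients"), and also by tumour type. It then plans "The 80% and 95% confidence intervals for difference in SUV" between GRPR positive and negative patients, by a t or rank-sum method; that sentence names no time variable. The SUV ratio to reference regions (SUVr) is calculated at each time point but only listed (SAP 7.2 and 11). The SAP does recognise that schedule matters between groups: "Dosimetry and non-dosimetry group will be summarized separately due to different scheduled time points".

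For the dosimetry group, Protocol 4.1.6 says that "imaging should begin at 15min, 1h±15min, 2h±15min and 4h±30min post IMP injection". Protocol 3.1 and SAP 2.2 also allow the non-dosimetry scan times to be moved for remaining patients once results from at least 3 dosimetry patients are available.

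**The concern.** A value labelled 1h30 can come from any minute between 1 h and 2 h, and one labelled 2h30 from any minute between 2 h and 3 h. If uptake is still changing then, part of the spread at a nominal time is timing. If one tumour type, or the GRPR-negative patients, happen to be scanned earlier within the window than the others, they will look different for that reason alone.

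This touches the main quantitative description in the study. Tumour/background SUV, overall and by tumour type, is part of the primary endpoint (Protocol 3.3.1, SAP 3.1), and lesion SUV is how SAP 7.2 evaluates targeting. Protocol 4.1.6 also wants SUV thresholds per tumour type and time point, and a time point an hour wide makes such a threshold less sharp.

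Unequal timing between groups is possible. Recruitment is competitive with no maximum per centre (Protocol 3.4.3), and the SAP does not consider centre effects (SAP 5.5). If centres schedule differently and recruit different tumour mixes, timing and tumour type become linked. A mid-study change of scan times could do the same if some tumour types recruit later. Nothing in the planned output would show whether this had happened.

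**Working it through.** No figure in the plan bears on scan timing, so there is none to reproduce.

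**Windows and gap** (Protocol 3.1, 4.1.6)

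- Early: 90 − 30 = 60 to 90 + 30 = 120 min.
- Late: 150 − 30 = 120 to 150 + 30 = 180 min.
- Shortest gap on paper: 120 − 120 = 0 min. With a 15-min acquisition, about 15 min start to start, if the windows refer to scan start (stated for the dosimetry group only).
- Longest gap: 180 − 60 = 120 min. Nominal gap: 150 − 90 = 60 min.

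**Where another time course exists.** The dosimetry windows are 15 min, 45–75, 105–135 and 210–270 min, which do not overlap. That group is 5 breast and 5 prostate patients. Colorectal, NSCLC and SCLC patients (10 + 10 + 10 = 30 of the 40 non-dosimetry patients) have only the two wide-window scans.

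**Noise at one nominal time.** The documents give no rate of change between 60 and 180 min, so a rate r per hour is assumed. Let SUV be proportional to (1 + r)^(t/60), with t uniform over the 60-min window. Then ln SUV is uniform over a width of |ln(1 + r)|, and the coefficient of variation (CV) from timing is approximately |ln(1 + r)|/√12.

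| Assumed r per hour | \|ln(1 + r)\| | CV from timing | Ratio, end to start of window |
|---|---|---|---|
| −30% | 0.357 | 10.3% | 0.70 |
| −10% | 0.105 | 3.0% | 0.90 |
| 0 | 0 | 0% | 1.00 |
| +10% | 0.095 | 2.8% | 1.10 |
| +30% | 0.262 | 7.6% | 1.30 |

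A simulation of one million uniform start times gave the same CVs.

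**Bias in a group comparison.** If mean scan times differ by d minutes between two groups, the apparent ratio from timing is (1 + r)^(d/60). For d = 20:

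- r = +10%: 1.10^(1/3) − 1 = +3.2%; r = −10%: 0.90^(1/3) − 1 = −3.5%.
- r = +30%: 1.30^(1/3) − 1 = +9.1%; r = −30%: 0.70^(1/3) − 1 = −11.2%.

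For d = 0 the bias is zero at any r.

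**The case against.** The strongest reply is that wide windows only add noise. Every non-dosimetry patient is scheduled for both scans, and the documents do not say that timing differs by tumour type or GRPR status. This stands: bias is a possibility the plan cannot check as written, not a demonstrated defect.

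Nor do the documents give a rate. Protocol 2.4 says of an earlier study that "there was a fast tumour-uptake, a rapid blood and renal clearance, which resulted in a good imaging performance as early as 60 minutes post-injection". A reader might infer that tumour/background must keep changing from 60 to 180 min. The sentence does not say so, and fast kinetics fit equally well with most of the change being over by 60 min. The zero row in the table is therefore a real possibility.

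Three further readings go too far.

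- A reader might infer that time and targeting cannot be separated. The plan does not separate them, but raw PET/CT image files go to the central imaging centre (Protocol 4.1.6), so actual times are probably recoverable.
- A reader might infer that SUVr is summarised at nominal times. It is only listed.
- A reader might infer that the early-to-late change in this group determines the imaging window for future trials. Protocol 3.1 and SAP 2.2 assign that question to the dosimetry data, and no early-to-late change is a planned endpoint.

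Reach is limited too. The number and location of lesions is not an SUV summary, positivity against conventional imaging is judged visually (SAP 7.4), and all testing is exploratory. These points lower the weight of the matter. They do not supply a reason to analyse SUV by scheduled time alone.

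**Conclusion.** The point holds as a shortcoming of the planned SUV analysis. Each nominal time point spans 60 min, the two scans may be from about 15 to 120 min apart, and SAP 7.2 makes no use of actual time in its SUV summaries or in the GRPR positive–negative difference.

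The size cannot be determined from the documents. At an assumed change of 10–30% per hour in either direction, with uniform timing in the window, timing adds a CV of about 3–10% at one nominal time. A 20-min difference in mean scan time between groups would shift a comparison by about 3–11%; with no such difference, or no change in uptake, there is no bias. The dosimetry time course cannot settle this for colorectal cancer, NSCLC or SCLC without assuming that their kinetics match those of breast and prostate cancer. The sample size rationale and the lesion-count endpoint are not affected. This is a cheap improvement that should be made before database lock.

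**What to change.** In SAP 7.2:

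1. Derive actual minutes from injection to scan start for every scan. This assumes that both times can be recovered from the recorded injection time and the image files; the sponsor should confirm it.
2. Show the median and range of actual minutes beside each nominal-time SUV summary, by tumour type and by GRPR status.
3. Plot lesion SUVmean, SUVmax and SUVr against actual minutes, by tumour type.
4. Wherever the GRPR positive–negative SUV difference is reported, add a sensitivity analysis that adjusts it for actual minutes, and state the time point to which each difference refers.
5. Apply the same steps to any scans re-timed under Protocol 3.1 and SAP 2.2, and say under which time-point label they will be summarised.

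The cost is one derived variable and a few additional outputs. No new procedure and no change to the scan schedule is needed, and SAP 1 allows revision before database lock.
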